## Form Content

### I. Project Introduction

**I.1** **Project to be reviewed by:**  
IRB-01

**I.2** **Project Title:**  
Transesophageal echocardiography (TEE): A novel technique for spinal cord imaging

**I.3** **Short Title (optional):**

**I.4** **Provide a short summary of the purpose and procedures of the study proposed in this IRB application.**

- **DO NOT include information on studies not proposed in this application.**
- **Use LAY terminology only. This must be easily understandable by IRB community members and nonscientists.**
- **DO NOT cut and paste technical abstracts from funding applications that may not be understood by a general audience.**

The aim of this prospective observational study is to assess whether transesophageal echocardiography (TEE) can be used to identify the structures within the vertebral foramen of the spinal column and to determine the range of spinal segments which can be visualized. Data will be collected from both pediatric and adult patients undergoing cardiothoracic and interventional cardiac surgeries under general anesthesia. Because use of TEE is a standard surgical procedure and because TEE will already be in place to visualize the heart, no additional processes will be required to collect data, minimizing patient risk. TEE will be monitored and controlled by a trained anesthesiologist or TEE technician and visualization of the spinal cord will be confirmed. Real-time TEE images will then be captured and later graded by a trained sonographer as high, medium or low quality. Starting at the level of the tracheal bifurcation, corresponding to thoracic vertebral level T5 (Mirajalili 2012), the TEE probe will be advanced cranially to determine the spinal levels visualized above T5 and caudally in order to determine the spinal levels below T5 that can be seen on TEE. At each level seen on TEE, pictures will be taken for confirmation.

**I.5** **Specify your research question(s), study aims or hypotheses (do not indicate "see protocol")**

The primary outcome is to identify the spinal column and epidural space on real-time TEE image, as well as to determine the range of spinal segments that can be visually spanned by TEE.

The secondary outcomes include classification of the captured TEE image as high, medium or low quality as determined by a trained sonographer.

H0: The null hypothesis is that the spinal cord and epidural space will not be visualized on real-time TEE image.

H1: The alternative hypothesis is that the spinal cord and epidural space will be successfully confirmed by real-time TEE image in all individuals.

To test this hypothesis, both pediatric and adult patients undergoing cardiothoracic or interventional cardiac surgeries under general anesthesia will be included in the study population.

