**DESCRIBE:**

- **What subjects will be asked to do/what happens in the study (in sequential order)**
- **The time period over which procedures will occur**
- **The time commitment for the subject for individual visits/procedures**
- **Long-term followup and how it occurs**

The subjects of the study, scheduled to undergo cardiothoracic or interventional cardiac surgeries, will only be asked to come to their surgery. The day of surgery the patients will not be required to do anything different from standard anesthesia and surgical practice at the hospital. Subjects will come to the operating room suite and the usual monitors (electrocardiogram, non-invasive blood pressure, and oxygen saturation) will be placed. Following the routine induction of anesthesia, the Mini-Multi TEE probe (Model T6207 (21381A), Philips, Bothell, WA, USA) will be advanced to mid esophageal level in order to visualize the heart, this is standard surgical procedure in these cases. Rotation of the probe by approximately 180 degrees toward the descending aorta, with an increased gain and depth decreased to 2-3 cm, will attempt to allow for appreciation of the spinal cord and epidural space. Upon confirmation of the structures within the vertebral foramen by a trained TEE operator, an images of the spine will be captured to be later graded as high, medium or low quality by a trained sonographer. The TEE probe will then be advanced caudally and intervertebral disc spaces will be counted in order to determine the number of spinal segments that can be spanned until an image can no longer be generated. This will take approximately ten minutes, but will occur while the patient is being prepared for surgery so no additional time in the operating room will be necessary. At this point, the TEE probe will be returned to mid esophageal level to visualize the heart and the operation will proceed as usual. When looking at patient medical records, we will only collect the following data: height, weight, age, any known history of esophageal abnormalities, lesions or disease and current procedure. Ten minutes is the approximate additional time that may be required intraoperatively to observe the spinal cord on TEE but this will not extend the time in the operating room and thus no additional billing is required. No additional visits or extra time is required of the subject. There will be no necessary long-term follow up or data collection. When the patient leaves the operating room, nothing additional is required.

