**XI.1 Describe the analysis methods you will use, including, if applicable, the variables you will analyze**

We are not planning to compare pediatric vs adult rates, we just want to observe the ability to image the spinal cord using TEE in this observational study. Thus, we will only use exploratory descriptive statistics for analysis.

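### The primary outcome names the spinal column, the hypotheses and analysis concern the spinal cord, and no rule says what must be seen for a level to count toward the range

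*Combined protocol and SAP*

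**What the plan says.** **Outcome (I.5).** The first part reads "The primary outcome is to identify the spinal column and epidural space on real-time TEE image". The second part reads "as well as to determine the range of spinal segments that can be visually spanned by TEE"; it does not name the structure that must be visible.

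**Hypotheses (I.5).** H0: "The null hypothesis is that the spinal cord and epidural space will not be visualized on real-time TEE image". H1 is that "the spinal cord and epidural space will be successfully confirmed by real-time TEE image in all individuals".

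**Aim (I.4).** The study asks whether TEE "can be used to identify the structures within the vertebral foramen of the spinal column".

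**Analysis and sample size (XI.1, XI.2).** XI.1 says "we just want to observe the ability to image the spinal cord using TEE in this observational study" and limits the analysis to descriptive statistics. XI.2 justifies 50 pediatric and 50 adult patients by the wish to confirm that the cord can be observed, and says there is no prior basis for a rate.

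**Counting the range (VII.E.6).** After a trained operator has confirmed the contents of the vertebral foramen and an image has been captured, the probe moves in the caudal direction. The counting rule reads: "intervertebral disc spaces will be counted in order to determine the number of spinal segments that can be spanned until an image". The sentence then ends the count at loss of that image. I.4 also describes a cranial scan, says that cord visualization is to be confirmed, and plans a picture at each level seen. VII.E.6 mentions neither the cranial scan nor the per-level pictures.

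**The concern.** Column and cord are different targets, and seeing the bony column does not establish that the cord was seen. Because the analysis is purely descriptive, the definition of a success is the result. If the outcome sentence and the hypotheses define success differently, the same images can give two answers, and the plan does not say which is reported.

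The range is exposed in the same way. Disc spaces belong to the column. A counting rule built on them, with a stopping point tied to an unspecified image, can carry the count past the last level at which the cord was visible. A reader of the results would take the range as one over which the cord can be imaged, since that is what the title and XI.1 announce.

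**Working it through.** This is a question of consistent definitions, so the main check is to set the sections side by side. There is no planned figure to reproduce: XI.2 gives no alpha, power, reference rate or expected rate.

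**1. Target structure by section**

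- I.2 title: spinal cord.
- I.4 aim: structures within the vertebral foramen.
- I.5 primary outcome: spinal column and epidural space.
- I.5 H0 and H1: spinal cord and epidural space.
- XI.1 and XI.2: spinal cord.

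The primary outcome sentence stands apart from the others on the first structure.

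**2. Which patients are classified differently**

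- Column, epidural space and cord all seen: meets the outcome and is consistent with H1.
- Column only: does not meet the outcome, because the epidural space is also required, and fails H1.
- Column and epidural space seen, cord not seen: **meets the outcome, fails H1**.

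Only the third pattern causes the conflict.

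**3. What one such patient does**

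With *d* patients of the third pattern in a group of *n*, the two definitions differ by d/n. For n = 50 this is 1/50 = 2 percentage points per patient; for all 100 patients it is 1 point.

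H1 is worded for all individuals, so d = 1 is enough to contradict it even if every patient meets the outcome. If *q* is the probability of the third pattern, the chance of at least one such patient is 1 − (1 − q)^n. The documents give no q; the values below are assumptions.

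- q = 1%: 1 − 0.99^50 = 1 − 0.605 = 39.5% in one group; 1 − 0.99^100 = 1 − 0.366 = 63.4% overall.
- q = 5%: 1 − 0.95^50 = 1 − 0.077 = 92.3% in one group; 1 − 0.95^100 = 1 − 0.006 = 99.4% overall.
- q = 10%: 1 − 0.90^50 = 1 − 0.005 = 99.5% in one group.

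A rare discordance would therefore probably be enough to separate the two readings.

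**4. The range**

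The sequence in VII.E.6 is: confirm the foramen contents at the starting position, capture an image, advance, count disc spaces, stop when no image is obtained. The confirmation precedes the sweep and is not repeated for each level. If *k* levels are counted and the cord is seen at *m* of them, the cord range is overstated by k − m levels. As an assumed illustration, k = 8 with m from 4 to 7 gives an overstatement of 1 to 4 levels. None of these inputs comes from the documents.

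**The case against.** The strongest reply is that *column* is loose wording for the contents of the column. I.4 speaks of structures within the vertebral foramen of the column, and VII.B.37 speaks of visualizing the column and then describes imaging those same contents. The probe settings in VII.E.6 are aimed at the cord and epidural space, and capture follows operator confirmation. The image that ends the count can naturally be read as the same kind of image. This is a fair account of what the investigators probably meant, and it supports correcting I.5 toward the cord. It does not supply a rule: no section says what must be seen for a structure to be confirmed or for a level to count. The later sonographer grading concerns image quality, not which structures are present.

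Three stronger readings are tempting, and the documents do not support them:

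- *Column views alone satisfy the primary outcome.* They do not; the outcome also requires the epidural space.
- *The true cord range could never be recovered.* I.4 plans a picture at each level seen, so cord visibility might be re-read from those pictures, if they are taken during the sweep.
- *The reported cord rate will be inflated.* Confirmation directed at the cord and foramen contents makes this less likely, and no rates are given from which to show it.

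**Conclusion.** The point holds as a conflict of definitions. The primary outcome and the hypotheses in I.5 name different structures, and the text allows a patient to meet one and fail the other. The counting rule in VII.E.6 allows a level to enter the range without the cord having been seen there. The existing safeguards lower the risk but set no criterion.

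The direction for the range is clear: any such level lengthens it. The size, for both the rate and the range, is unknown. The figures above show only how sensitive the result would be under assumed discordance; they are not estimates. The conclusion rests on reading the outcome sentence and the counting rule as written. It should be settled before images are read, since the whole result is descriptive and depends on what counts as seen.

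**What to change.** - **I.5:** replace *spinal column* with *spinal cord* in the primary outcome, so that it matches H0 and H1, and have XI.1 report on that same target.
- **I.4 and VII.E.6, cranial and caudal scans alike:** use disc spaces only to number the levels. At each level record cord yes/no and epidural space yes/no, checked against the picture for that level.
- **Range:** count toward the primary range only levels at which the target structures are seen. Report any gaps between such levels. Report the disc-space span separately, as visibility of the column.

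The cost is one tick per structure per level on the data sheet and a few changed sentences. No further patients are needed, and the per-level pictures are already planned in I.4. The drawback is that the reported range may be shorter.

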**I.6** **Background and significance and/or Preliminary studies related to this project. (do not indicate "see protocol")**

Transesophageal echocardiography is a semi-invasive, monitoring and analytic tool used to generate reproducible images of the heart and mediastinum. TEE is routinely used in cardiothoracic and interventional surgeries as well as in detecting thromboses, valvular defects and congenital heart disease. There has been expanding utilization of TEE outside of cardiac surgery as a potential haemodynamic monitor both intraoperatively and postoperatively (Pissarra 2012). While TEE is not regularly used to visualize the spinal column, it can be done with relative ease when consciously attempted (Chitilian 2006). To our knowledge, this prospective observational study will be the first attempt to deliberately image the structures within the vertebral foramen, to scan the spinal segments identified by TEE and to classify the TEE image quality by a trained sonographer. Given the nearly universal use of TEE in cardiac surgical operating rooms, in combination with the low risk of complications (Daniel 1991), potential outcomes include the use of TEE in the placement of thoracic epidural catheters, in identification of spinal cord trauma or as a monitor of intraoperative perfusion and pressure surrounding the spinal cord (Godet 1994). This could lead to improved precision, success and safety of regional anesthesia.

**II.3 The Principal Investigator of this study is:**  
Faculty

## III. Funding/Other Support

**III.1 Funding Sources**

Type	Source	Grant Title	Name of PI on Grant
Departmental / PI Discretionary			
* new source name			

**III.3 Does any member of the research team have a financial conflict of interest related to this project according to the [Conflict of Interest in Research](#) policy? If yes, please indicate which members below.**

Name	Has Conflict of Interest
[name]	No

**Do you want the IRB to give this project**  
Regular (expedited or full board) review

## IV. Project Type

**IV.1**

**IV.2 Enter the date you will be ready to begin screening subjects/collecting data for this project. (If you do not have a specified date, add "upon IRB approval")**  
6/25/2012

**IV.3 Are you requesting a [waiver of informed consent/authorization](#) (subjects will not be given any oral or written information about the study)?**  
No

## V. Other Committee Review

**V.1 Does this project involve any substance ingested, injected, or applied to the body?**

- Do not answer yes, if the involvement includes a device, wire, or instrument

No

**V.2 Are any contrast agents used for any purpose in this study?**

No

**V.9 Will any subject be asked to undergo a diagnostic radiation procedure (including radiographic, nuclear medicine, DEXA)?**

No

**V.14 Will any subject be asked to undergo a radiation therapy procedure (including external beam therapy, brachytherapy, or nuclear medicine therapy)?**

No

**V.20 Does this project involve the deliberate transfer of recombinant or synthetic nucleic acid molecules, or DNA or RNA derived from recombinant or synthetic nucleic acid molecules, into one or more human research participant?**

No

**V.21 Will any portion of this project be conducted in the CRU, or does it use any CRU resources?**

No

**V.22 Will this project use any resource/patients of the HCCC?**

No

**V.23 Will any part of this project be conducted on VAMC premises?**

No

**V.24 Does this project involve VAMC patients or records?**

No

**V.25 .a Will the study involve any of the following activity at UI Health Care, even if subjects or their insurance will not be billed for the item or service, and regardless of the study funding source (including studies with departmental or no funding)?**

- Procedures, tests, examinations, hospitalizations, use of Pathology services, use of clinic facilities or clinical equipment, or any patient care services, including services conducted in the Clinical Research Unit; or
- Physician services or services provided by non-physicians who are credentialed to bill (ARNPs, Physician Assistants, etc.)

Yes

**V.26 The study involves nursing, nursing resources or evaluates nursing practices.**

No

## VI. Subjects

**VI.1 How many adult subjects do you expect to consent or enroll for this project?**

50

**VI.2 What is the age of the youngest adult subject?**

18.0

**VI.3 What is the age of the oldest adult subject?**

90.0

**VI.4 What is the percentage of adult male subjects?**

50

**VI.5 What is the percentage of adult female subjects?**

50

**VI.6 How many minor subjects do you expect to consent or enroll for this project?**

50

**VI.7 What is the age of the youngest minor subject?**

0.0

**VI.8 What is the age of the oldest minor subject?**

17.0

**VI.9 What is the percentage of minor male subjects?**

50

**VI.10 What is the percentage of minor female subjects?**

50

**VI.11 Will any of the minors enrolled be in foster care or Wards of the court?**

No

**VI.13 Describe EACH of your subject populations**

- **Include description of any control group(s)**
- **Specify the Inclusion/Exclusion criteria for EACH group**
- **Studies under IRB-03 enrolling non veterans as part of the subject population must present a compelling argument to the IRB for the inclusion of non-Veterans (e.g., insufficient number of Veterans; survey of VA employees; study of active duty military; study involving Veterans' family members), and the research is relevant to the care of Veterans or active duty military personnel.**

The study populations will include 50 pediatric patients and 50 adult patients scheduled for cardiothoracic or interventional cardiac surgeries under general anesthesia. We will exclude any patients with known esophageal abnormalities, lesions or disease that would disqualify the patient for the use of TEE as standard procedure. We will also exclude any patients that come to the catheter laboratory exclusively for TEE exam as our study will only occur in patients already scheduled to undergo TEE use in surgery or diagnostic procedure. This will ensure that our study occurs only as a part of standard procedure and will not lengthen time under anesthesia or time in the operating room. There is no control population needed.

**VI.14 Provide an estimate of the total number of subjects that would be eligible for inclusion in each of your study populations (include your control population if applicable)**

50 pediatric patients and 50 adult patients. There is no control population needed. We expect to complete this study in one year.

**VI.15 Describe how you will have access to each of your study populations in sufficient number to meet your recruitment goals.**

Outpatient pediatric and adult cardiac surgery patients will be recruited at the cardiology clinics when patients visit for the preoperative evaluation. Inpatient cardiac patients will be identified initially by using the EPIC operating room schedule on the day before surgery. We will have access to these populations by working within the Department of Anesthesiology, and by monitoring the OR schedule for patients scheduled to undergo cardiothoracic or interventional cardiac diagnosis and surgeries. The use of TEE is standard procedure for visualizing the heart in these procedures. A trained TEE operator will be available to control and capture images. Patients will be recruited until data has been collected in 50 pediatric patients and 50 adult patients.

**VI.16 Do you plan to recruit/enroll non-English speaking people?**

No

**VI.18 Do you propose to enroll any of the following in this study as subjects?**

- **Employee of the PI or employee of a research team member**
- **Individual supervised by PI or supervised by member of research team**
- **Individual subordinate to the PI or subordinate to any member of the research team**
- **Student or trainee under the direction of the PI or under the direction of a member of the research team**

No

**VI.20 Will subjects provide any information about their relatives?**

No

**VI.23 Will anyone (other than the subject) provide you with information about the subject (e.g. proxy interviews)?**

No

**VI.26 Is this project about pregnant women?**

No

**VI.27 Will this project involve fetuses?**

No

**VI.28 Does this project involve adult subjects who may be incompetent or have limited decision-making capacity on**

**initial enrollment into the study?**

No

**VI.32 Does this project involve subjects whose capacity to consent may change over the course of the study?**

No

**VI.37 Does this project involve prisoners as subjects?**

No

## VII.A. Project Description (A)

**Where will project procedures take place (check all that apply)?**

- UIHC - Main Operating Rooms, Pediatric Catheter Laboratory, Pediatric and Adult Cardiac Surgery Clinics

**Is this project also being conducted by other researchers at their own sites (e.g. a multi-site collaborative project)?**

No

## VII.B. Project Description (B)

**VII.B.1 Does this project involve any of the following:**

- **clinical intervention**
- **pharmacologic intervention**
- **therapeutic intervention**
- **physiology studies (e.g. studying the functions of organs, tissues, or cells)**

Yes

**VII.B.2 Does this project involve a drug washout (asking subject to stop taking any drugs s/he is currently taking)?**

No

**VII.B.6 Will any subjects receive a placebo in this study when, if they were not participating, they could be receiving an FDA-approved treatment for their condition?**

No

**VII.B.11 Is there a separate, written protocol that will be submitted in addition to this IRB New Project form? (Note: a grant application is not considered to be a protocol)**

No

**VII.B.18 Does this project involve testing the safety and/or efficacy of a medical device?**

Yes

**VII.B.19 Describe in detail procedures in place for maintaining device shipment and receipt records:**

This device is already onsite being used in the UIHC Main Operating Room and Pediatric Catheter Laboratory of alternative purposes, thus, no device shipping or receipt will occur.

**VII.B.20 Who will be responsible for maintaining these shipment and receipt records?**

N/A

**VII.B.21 Describe in detail procedures in place for tracking use and disposition of devices described in this study:**

N/A

